1.2.5. BENEFITS AND RISK ASSESSMENT

Although a number of treatment options are available for RA, there remains a clear need for novel therapeutics. Many patients do not benefit optimally from the available small molecule and biologic drugs, leaving opportunity for differentiated drugs with new modes of action and an improved safety profile.

Considering the importance of IL-6 in chronic inflammatory diseases, several companies are developing drugs that target this pathway, and multiple clinical studies have demonstrated that treatment with IL-6 pathway inhibitors can improve

manifestations of RA. ALX-0061, administered i.v. and in combination with MTX, has been shown to be effective in reducing signs and symptoms for the treatment of subjects with active RA.

The current study is designed to evaluate the efficacy and safety of ALX-0061, administered s.c. in subjects with active RA, who have had an inadequate response to methotrexate (subjects from study ALX0061-C201), or who are intolerant to MTX or for whom continued MTX is inappropriate (subjects from study ALX0061-C202). Potential candidates for this study are required to have objective evidence of active disease.

The Sponsor is studying s.c. administration in an effort to develop a route of administration which will offer an alternative and more convenient option for administration, while maintaining its clinical efficacy and safety profile. Details on the design of, and rationale for, the current study are available in section [3.1.1](#) of the protocol.

An assessment of potential risks associated with inhibition of the IL-6 pathway, or inherent to the administration of therapeutic proteins, is described below. IL-6 is a pleiotropic cytokine with an important role in a broad spectrum of biological events, therefore, potential risks related to inhibition of the IL-6 pathway, as well as potential risks inherent to the administration of therapeutic proteins, are considered.

- Inhibition of the IL-6 pathway has immunomodulatory effects, and has been reported to increase the risk for infection [\[15, 16\]](#). So far, serious infections have not been reported for ALX-0061.
- Suppression of IL-6 activity is known to reduce the levels of acute phase proteins such as CRP, SAA and fibrinogen [\[17, 18\]](#).

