3.3.5. PRIOR AND CONCOMITANT THERAPY

Prior and concomitant medication are documented throughout the study.

During the 104-week treatment and assessment period of the study, subjects are not allowed to initiate DMARDs (other than MTX for subjects who completed the preceding Study ALX0061-C201, see below).

Permitted Medication

Subjects who completed the prior combination therapy study (Study ALX0061-C201) will receive ALX-0061 and will be recommended to continue

with MTX, while subjects who completed the prior monotherapy study (Study ALX0061-C202; except those who were assigned to TCZ) will receive ALX-0061 as monotherapy.

MTX will not be considered one of the study agents and the MTX dose can be adjusted at the Investigator's discretion.

Commercially available MTX will be used in this study and will not be provided by the Sponsor. Continued supplementation with oral folic acid or oral folinic acid should be given at the discretion of the treating physician for patients on MTX.

Subjects treated with NSAIDs (including aspirin and selective cyclooxygenase 2 inhibitors) and other analgesics (except high-potency opioid analgesics; see prohibited medication) should receive the usual marketed doses approved in the country in which the study is being conducted, and should be on a stable dose whenever possible until the Week 104 visit, or until the Early Termination Visit. Changes in the dose may be done at the discretion of the Investigator if he/she feels it is medically justified. Whenever possible, short-acting NSAIDs and other analgesics should not be administered within 6 hours before study assessments. Long-acting ones can be maintained at their usual dosing intervals before study assessments.

Subjects treated with oral corticosteroids should receive a stable dose equivalent to ≤ 10 mg of prednisone/day, up to and including Week 104, or until the Early Termination Visit. The dose of oral corticosteroid may be changed at the discretion of the Investigator.

The number of intra-articular (i.a.) corticosteroid injections is limited to 2 injections over a 104-week period. The joint(s) affected by the procedure(s) will be considered as swollen and tender for 28 days/4 weeks in the data analyses from the date of the procedure onward.

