The use of concomitant medication will be evaluated at Weeks 0, 4, 8, and 12, and every 12 weeks thereafter; however, treating physicians should monitor MTX and other therapies in accordance with appropriate clinical guidelines.

The expression of hepatic CYP450 enzymes is suppressed by IL-6. IL-6 blocking might therefore influence (normalize) CYP450 expression and products that are substrates for CYP450 enzymes (e.g., statins, warfarin, theophylline, oral contraceptives, calcium antagonists phenytoin, cyclosporine, benzodiazepines) could be metabolized faster. Subjects taking medicinal products which are metabolized via CYP450 3A4, should be closely monitored and their treatment might have to be adapted if necessary in order to maintain therapeutic efficacy. Subjects on warfarin will be monitored by assessment of INR (see [Schedule of Assessments](#)); the lipid levels will be evaluated which will be of help to monitor the

subjects on statins (see [Schedule of Assessments](#)). If needed, the Investigator or the relevant treating physician should adapt the treatment of the concerned subject (unscheduled visits can be planned upon the discretion of the treating physician). Given the long half-life of ALX-0061, the influence on the hepatic enzymes can persist for several weeks.

Other medication (e.g., to treat AEs) may only be prescribed after consultation with the Investigator, unless in case of an emergency situation that does not allow discussion.

Prohibited Medication

The following medications are prohibited during the study (up to and including Week 104 or Early Termination Visit):

- DMARDs (other than MTX for subjects who completed the preceding Study ALX0061-C201).
- Intramuscular (i.m.) administration of corticosteroids for the treatment of RA. In this study, oral corticosteroids can be increased to 10 mg/day. For i.a. dosing see "permitted medication".
- High-potency opioid analgesics, including but not limited to hydrocodone, metopon, oxycodone, clonitazene, hydromorphone, oxymorphone, morphine, fentanyl, levorphanol, buprenorphine, methadone, meperidine.
- Use of, any biological DMARD, targeted synthetic DMARD (such as tofacitinib), or investigational drugs.
- Use of any live attenuated vaccine.

Contraceptives

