**Baseline disease characteristics:**

Please refer to the efficacy section 12.3 for detailed definitions of the parameters. Below baseline parameters will be extracted from the parent study and calculated parameters will not be recalculated.

- Swollen joint count (SJC66): number of swollen joints out of 66 assessed joints
- Tender joint count (TJC68): number of tender joints out of 68 assessed joints
- Swollen joint count (SJC28): number of swollen joints out of 28 assessed joints used for DAS28 calculation
- Tender joint count (TJC28): number of tender joints out of 28 assessed joints used for DAS28 calculation
- Tender joint count categories (<10, 10-20, >20)
- Swollen joint count categories (<7, 7-11, >11)
- CRP (mg/dL)
- CRP categories (<= upper limit of normal range [ULN], >ULN and <=1.2xULN, >1.2xULN and <=3xULN, >3xULN)
- ESR (mm/h)
- Physician's global assessment of the disease (VAS; 0-100 mm)
- Patient's global assessment of the disease (VAS; 0-100 mm)
- Patient's assessment of pain (VAS; 0-100 mm)
- HAQ-DI (0-3)
- SF-36 Physical component summary
- SF-36 Mental component summary
- Time since first RA symptoms (years)
- Time since RA diagnosis (years)
- ACR functional class at screening (of parent trial): class I / class II / class III / class IV
- Extra-articular symptom location: any of the following: skin, eyes, gastrointestinal, heart, lung, renal, nervous system, other
- Extra-articular symptoms: only listed
- Rheumatoid factor (RF) concentration (kIU/L)
- RF category (positive [>ULN], negative [<=ULN])
- Anti-CCP category (positive [>ULN], negative [<=ULN])
- Combined RF and anti-CCP category (double positive, double negative, mixed negative and positive)
- DAS28 Score (ESR)
- DAS28 Score (CRP)
- DAS28(ESR) and DAS28(CRP) categories (<=3.2, >3.2 and <=5.1, >5.1)
- Clinical Disease Activity Index (CDAI)
- Simplified Disease Activity Index (SDAI)
- MTX use (dose)

- Corticosteroid use (prednisone equivalent dose)
- Duration of morning stiffness (minutes)
- FACIT

A detailed list of tables and listings can be found in section 13.1 and section 15.1, respectively.

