#### **5.6 Concomitant Therapies**

Any concomitant therapy taken during the study will be recorded in the eCRF, including ongoing concomitant therapies from the parent trial. Concomitant therapies are defined as therapies with a stop date on or after date of first dose of study drug in the C203 study. Therapies stopped before the study are not recorded. Analysis of prior medications is available in the parent trials.

All therapies are coded using the latest WHO-DRUG version. No anatomical therapeutic chemical classification system (ATC) selection is performed.

Concomitant therapies will be tabulated by generic term, for RA and non-RA medications separately, by treatment group and overall using the ITO population. Multiple records of the same generic term for the same subject will be counted only once. The table will therefore present subjects, not occurrences. The tables are sorted by decreasing frequency based on all subjects.

Systemic corticosteroids are selected as steroid RA-therapy with intravenous or intramuscular administration (not intra articular)

A detailed list of tables and listings can be found in section 13.1 and section 15.1, respectively.

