## 6 EFFICACY

### 6.1 Main Efficacy Analysis

No inferential statistical analyses will be performed. All tables will be presented by treatment group and overall, including treatment groups defined by previous dosing regimen of the parent trial (cfr. section 4.2.2). All analyses will be run on the ITO. The main analysis will be on observed cases (OC).

Continuous efficacy endpoints will be summarized as follows:

- Actual values: descriptive statistics (mean, 95% CI on the mean [normal approximation], SE, median, minimum, and maximum) per endpoint and time point. The baseline value from the parent trial will be included to the summary, if applicable.
- Changes from baseline: baseline adjusted LS means and 95% CI from an ANCOVA model with treatment as factor and baseline as covariate, median, minimum and maximum per endpoint and post-baseline time point.

This will be done for the following parameters: ACR-N, DAS28(CRP), DAS28(ESR), SDAI, CDAI, HAQ-DI, SF-36 physical and mental component scores, FACIT-Fatigue, duration of morning stiffness, patient's assessment of pain (VAS-scale), patient's global assessment of disease activity (VAS-scale), physician's global assessment of disease activity (VAS-scale), CRP, ESR, TJC68, TJC28, SJC68, SJC28, MTX dose, corticosteroids dose. Different types of systemic corticosteroids will be converted to Prednisolone equivalent doses before calculating the cumulative dose of corticosteroids. The cumulative dose will be given in mg/day (Please refer to Appendix 2 section 16.2 for more details).

Categorical efficacy endpoints will be presented using a frequency tabulation of the parameter at each time point, including a Wilson score 95% CI on the percentage of subjects in the category of interest. The baseline value from the parent trial will be included to the summary, if applicable. This will be done for the following parameters: ACR20, ACR50, ACR70, EULAR response (including EULAR good response), DAS28(ESR) low disease activity / remission / maintained remission / maintained low disease activity, DAS28(CRP) low disease activity / DAS(CRP) < 2.6 / maintained DAS(CRP) < 2.6 / maintained low disease activity, SDAI low disease activity / remission / maintained remission, CDAI low disease activity / remission / maintained remission, Boolean remission / maintained remission, HAQ-DI clinically meaningful improvement, HAQ-DI normal physical function, MTX dose reduction rate, MTX discontinuation rate.

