- Disease activity is defined as follows based on the actual value of DAS28(ESR):
  - Remission:  $DAS28(ESR) < 2.6$
  - Low disease activity:  $2.6 \leq DAS28(ESR) \leq 3.2$
  - Moderate disease activity:  $3.2 < DAS28(ESR) \leq 5.1$
  - High disease activity:  $DAS28(ESR) > 5.1$
  - Pooled category Remission + Low disease activity will be shown as well
- Disease activity is defined as follows based on the actual value of DAS28(CRP):
  - $DAS28(CRP) < 2.6$
  - Low disease activity:  $2.6 \leq DAS28(CRP) \leq 3.2$
  - Moderate disease activity:  $3.2 < DAS28(CRP) \leq 5.1$
  - High disease activity:  $DAS28(CRP) > 5.1$
  - Pooled category  $DAS28(CRP) < 2.6$  + Low disease activity will be shown as well
- Boolean remission is defined as follows:
  - Yes:  $TJC28 \leq 1 \text{ AND } SJC28 \leq 1 \text{ AND } VASPA \leq 1 \text{ cm AND } CRP \leq 1 \text{ mg/dL}$
  - No: else
- Clinically meaningful improvement in HAQ-DI (clinically meaningful improvement from baseline – absolute change) is defined as follows:
  - Yes:  $\Delta HAQDI \geq 0.25$
  - No:  $\Delta HAQDI < 0.25$

- Normal physical function based on HAQ-DI is defined as follows:
  - Yes:  $HAQDI \leq 0.5$
  - No:  $HAQDI > 0.5$
- CDAI score = TJC28 + SJC28 + VASPA (cm) + VASPHA (cm)
- CDAI classification:
  - Remission:  $CDAI \leq 2.8$
  - Low disease activity:  $2.8 < CDAI \leq 10$
  - Moderate disease activity:  $10 < CDAI \leq 22$
  - High disease activity:  $22 < CDAI$
  - Pooled category Remission+Low disease activity will be shown as well
- SDAI score = TJC28 + SJC28 + VASPA (cm) + VASPHA (cm) + CRP (mg/dL)
- SDAI classification:
  - Remission:  $SDAI \leq 3.3$
  - Low disease activity:  $3.3 < SDAI \leq 11$
  - Moderate disease activity:  $11 < SDAI \leq 26$
  - High disease activity:  $26 < SDAI$
  - Pooled category Remission+Low disease activity will be shown as well
- Maintained remission at Week x: remission at Week x and all consecutive time points.

MTX and corticosteroid dose related endpoints will be derived as follows:

- MTX dose decrease from baseline at W0, W48 and W104:
  - Yes: daily dose at Week 0/ Week 48 / Week 104 visit < baseline dose
  - No: else
- Discontinuation of MTX dose at W0, W48 and W104:
  - Yes: daily dose at Week 0/ Week 48 / Week 104 visit = 0
  - No: else
- Change from baseline of MTX dose at Week 0/ Week 48 / Week 104
- Change from baseline of corticosteroid dose at Week 0/ Week 48 / Week 104

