## 16.2 Appendix 2: Prednisolone equivalent dose chart

	Approx. equivalent dose (mg/day)*	Conversion factor
Cortisone	25	0.20
Hydrocortisone	20	0.25
Methylprednisolone	4	1.25
Prednisolone	5	1.00
Prednisone	5	1.00
Triamcinolone	4	1.25
Betamethasone	0.70	7.15
Dexamethasone	0.75	6.67
Deflazacort	6	0.83

\* Based on Prednisolone dose of 5 mg/day.

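### The steroid-dose endpoint, as defined, leaves out permitted oral steroids, and the MTX reduction and discontinuation rates do not require MTX at baseline

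*SAP*

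**What the plan says.** **Steroids.** SAP 5.6 states: "Systemic corticosteroids are selected as steroid RA-therapy with intravenous or intramuscular administration (not intra articular". The term appears again only in SAP 6.1: "Different types of systemic corticosteroids will be converted to Prednisolone equivalent doses before calculating the cumulative dose of corticosteroids". That dose is reported in Table 14.2.1.13.4. SAP 12.3 and the table entry name no route. The baseline item in SAP 5.3, "Corticosteroid use (prednisone equivalent dose", names none either. SAP Appendix 2 converts nine agents in mg/day, with the footnote "Based on Prednisolone dose of 5 mg/day".

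Protocol 3.3.5 permits oral use: "Subjects treated with oral corticosteroids should receive a stable dose equivalent to ≤ 10 mg of prednisone/day". It lets the investigator change that dose. Its list of prohibited medication includes "Intramuscular (i.m.) administration of corticosteroids for the treatment of RA".

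**MTX.** SAP 12.3 counts a subject as having discontinued as follows: "Yes: daily dose at Week 0/ Week 48 / Week 104 visit = 0". Reduction means a dose below the baseline dose. Everyone else is 'No' under both rules. Tables 14.2.1.13.1 and 14.2.1.13.2 use the ITO population. SAP 4.2.2 lists the C202 columns, and SAP 4.2.3 requires a grand total in every table. Protocol 1.2.5 describes the C202 subjects as those "who are intolerant to MTX or for whom continued MTX is inappropriate (subjects from study ALX0061-C202", and Protocol 3.3.5 has them on monotherapy in the extension.

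**The concern.** The steroid rule omits the route that the protocol permits and names one that it prohibits for RA. If it is programmed as written, the on-study dose in Table 14.2.1.13.4 would be close to zero. Real tapering of oral steroids would then be invisible. If the parent-study baseline does include oral use, a large fall would appear that never happened.

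The MTX rules meet a group that should not be taking MTX. An absent MTX record can be read in three ways: as dose 0, as missing (and so outside the denominator under SAP 4.3.1), or as 'No' under the else clause. The SAP does not choose, so the C202 cells and the pooled column depend on a programming decision.

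No single default suits both parent studies. SAP 5.6 says that therapies stopped before the extension are not recorded. A C201 subject who stopped MTX before Week 0 therefore has the same empty C203 record as a C202 subject who was not on it.

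**Working it through.** The plan gives no figure to reproduce here, so the rules are applied as written.

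**Inputs.** From the documents: a maximum of about 501 subjects (Protocol 3.6.8, SAP 3.2), the rules in SAP 12.3, and the Wilson interval named in SAP 4.3.1. Assumed, because the documents do not give them: a C202 share of 25%, 30%, 37.5% or 40%, and C201 rates of 10% discontinued and 20% reduced.

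**1. 'All subjects' MTX discontinuation.** Let x be the C201 discontinuers, n1 the C201 subjects and n2 the C202 subjects.
- No record = 0: (x + n2)/501
- No record = missing: x/n1
- No record = 'No': x/501

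| C202 share | n1 / n2 | x | = 0 | = missing | = 'No' |
|---|---|---|---|---|---|
| 25% | 376 / 125 | 38 | 163/501 = 32.5% | 38/376 = 10.1% | 38/501 = 7.6% |
| 30% | 351 / 150 | 35 | 185/501 = 36.9% | 35/351 = 10.0% | 35/501 = 7.0% |
| 37.5% | 313 / 188 | 31 | 219/501 = 43.7% | 31/313 = 9.9% | 31/501 = 6.2% |
| 40% | 301 / 200 | 30 | 230/501 = 45.9% | 30/301 = 10.0% | 30/501 = 6.0% |

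At a 30% share the Wilson 95% intervals are 32.8 to 41.2, 7.3 to 13.6 and 5.1 to 9.6. The C202 column itself reads 100%, empty or 0%.

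**2. 'All subjects' MTX reduction.** With no record = 0, the test for a C202 subject is 0 < 0, which is false, so the answer is 'No'. The pooled rate is 75/501 = 15.0%, 70/501 = 14.0%, 63/501 = 12.6% or 60/501 = 12.0%. With no record = missing it stays near 20% (70/351 = 19.9% at a 30% share).

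At a 30% share, no record = 0 therefore prints 36.9% discontinued beside 14.0% reduced. Among MTX users this cannot happen, because everyone who discontinues has also reduced.

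**3. C201 subjects who stopped before the extension.** Take 351 C201 subjects with 35 discontinuers, and assume k = 4, 7 or 11 of them stopped before Week 0. The true rate is 35/351 = 10.0%.
- No record = missing: (35 − k)/(351 − k) = 31/347, 28/344, 24/340 = 8.9%, 8.1%, 7.1%
- No record = 'No': (35 − k)/351 = 31/351, 28/351, 24/351 = 8.8%, 8.0%, 6.8%

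**4. MTX dose-change ANCOVA (Table 14.2.1.13.3).** SAP 4.2.1 requires both a baseline and a later value, so C202 enters only if both are stored as 0. In that case the overall mean baseline falls by share × 15, for an assumed C201 mean of 15 mg/week. With an assumed slope of −0.2 and LS means taken at the overall mean baseline, the shift is 0.2 × share × 15 = 0.75, 0.90, 1.13 or 1.20. A true C201 LS mean of −1.5 mg/week would read about −0.75, −0.60, −0.38 or −0.30.

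**5. Steroids.** Consider a subject on a stable oral dose of 10 mg/day throughout. On study the i.v./i.m. filter returns 0.
- Same filter at baseline: change = 0 − 0 = 0
- Parent baseline includes oral use: change = 0 − 10 = −10 mg/day

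In the second case the spurious mean change is −p × d. With p = 0.3 to 0.6 of subjects on d = 5 to 10 mg/day (assumed), it runs from −0.3 × 5 = −1.5 to −0.6 × 10 = −6.0 mg/day. The documents do not show which case applies.

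**The case against.** **The steroid sentence may not govern the endpoint.** It sits in the concomitant-therapy section, while SAP 6.1 points to SAP 12.3 for efficacy derivations and to Appendix 2 for conversion, and neither limits the route. Together with the route-free baseline item, this makes a wording slip likely. That much stands. But the shared term links the two sections, no other output uses it, and nothing in the SAP corrects it. SAP 11, on changes from the protocol, is silent.

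**Keeping the i.m. route is not an error in itself.** A dose measure should capture prohibited steroids that were actually taken. This is right; the fault is the missing oral route.

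**For MTX, the natural reading is that C202 has no value.** The main analysis uses observed cases, missing values leave the denominator, and a C202 column at 100% would be caught at output review. This is a reasonable expectation, and it leads to the figure near 10%. The SAP does not state it, though, and the else clause competes with it.

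**Pre-extension stoppers can be recovered.** Parent-study MTX data are needed anyway for baseline and Week 0. True, but the SAP does not say that they settle later status.

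**The stakes are low.** SAP 3.3 says that the protocol defines no primary or secondary endpoints and does not itself list MTX or steroid dose. SAP 6.1 plans no inference. This is accepted. SAP 6.1 does include these parameters in its main efficacy list, with confidence intervals.

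**Conclusion.** Both points hold. The steroid rule, followed literally, gives a wrong result: on-study dose near zero, and a change from baseline that is either blind to oral tapering or spuriously negative. The MTX rules leave the C202 and 'All subjects' cells undetermined. In the 30% example the pooled discontinuation rate is 36.9%, 10.0% or 7.0% from the same data.

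The mechanisms come from the text. The C202 share, the event rates, the number of early stoppers, the ANCOVA inputs and the steroid-use figures are assumptions, and the ANCOVA shift and the negative steroid change each need a further condition on how data are stored. C202 coding does not touch the C201 columns of the MTX frequency tables, although those columns can lose subjects who stopped before the extension. Oral steroid records would still appear in Table 14.1.2.3 and Listing 16.2.2.3. The damage is confined to supplementary descriptive tables, but it should be fixed because the correction is cheap.

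**What to change.** - **SAP 5.6 and 6.1:** reconcile the steroid selection with Protocol 3.3.5 so that the dose endpoint counts every systemic route actually taken, including oral and excluding intra-articular. Apply the same routes at parent-study baseline and on study. This concerns what is measured, not what is allowed.
- **SAP 12.3 and Tables 14.2.1.13.1 to 14.2.1.13.3:** restrict to C201 subjects with a parent-baseline MTX dose above 0. Show C202 and 'All subjects' as not applicable, or omit them as a stated exception to SAP 4.2.3.
- **Coding:** set the dose to 0 when a stop is recorded, whether in C203 or earlier in the parent study. Set an unknown dose to missing, not to 'No'.
- **Optional:** say that the cumulative steroid dose in mg/day means the total daily dose at the visit, summed over concurrent steroids.

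The cost is wording in three SAP sections, one population filter and a footnote on three tables. No new data are collected; parent-study records are needed for MTX stopped before the extension.
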